7.4.6.4 Return or Destruction of the Test Article

Usually, investigative substances are consumed in the experiments. Investigative substances not consumed by the experiments are disposed of in accordance with the policies of Environmental Health and Safety of Penn State. Some substances (e.g. protein or peptide-based) are autoclaved prior to disposal.

7.4.6.5 Prior and Concomitant Therapy

NA

8.0 Subject Numbers and Statistical Plan

8.1 Number of Subjects

Number of subjects to be enrolled: 25

Number of subject needed to complete study: 15

8.2 Sample size determination

Based on our previously published data 46, 115, 128, and data from our current cheese intervention study, we calculate that 14 subjects per group will be necessary to physiologically relevant differences between dietary interventions of at least 15%; (ANOVA, power=0.80, $\alpha=0.05$).

Our published data examining within-group differences between microdialysis drug treatments (using similar localized microdialysis drug treatments) suggest that within groups with compromised vasodilatory function, sample sizes of 8 and 7 subjects per group would be sufficient to detect a meaningful difference (effect size of 15%) between microdialysis treatment sites examining particular pathways (1 sample t-test, e.g., NO-dependent dilation). Our data specific to dietary cheese and sodium interventions indicates that 8 subjects are necessary find a meaningful physiological difference.

We suggest testing 15 subjects through all of the dietary interventions. We would plan to perform preliminary analyses after testing 8 subjects to reach our desired statistical power for detecting within group differences between microdialysis sites.

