FMD assesses conduit vessel endothelial function. We place a BP cuff on a forearm, gel on the upper arm just above the elbow, and a Doppler ultrasound probe on the gel. The ultrasound measures vessel size and blood velocity. After a 3-minute “resting” measurement, the cuff inflates for 5 minutes to occlude forearm BF. After the cuff deflates, we perform a second reading. We may repeat this measure several times.

Sublingual nitroglycerin: This procedure assesses vascular smooth muscle function. A nurse administers the sublingual nitroglycerine and is present throughout the procedure. The subject is supine on a medical bed or recliner. We apply a blood pressure / heart rate monitor (Cardiocap). We may take manual blood pressures. Also, we perform ultrasonography at the brachial artery at the elbow during the procedure. We place a 0.4 mg nitroglycerin tablet under the subject's tongue. The subject closes the mouth immediately after we insert the tablet. The tablet dissolves in 15-90 seconds. The subject refrains from swallowing until the tablet dissolves. Nitroglycerin causes blood vessels to dilate. The effects last for 5-10 minutes. The subject remains supine for 20 minutes following the nitroglycerin administration. The subject remains in the lab until 20 minutes after administration of the nitroglycerin. If the subject has an exceptional reaction to the nitroglycerin (e.g. drop in blood pressure with longer duration), we monitor the subject for up to 60 minutes following nitroglycerin administration.

b. MD: Local Heating

We prepare 4 MD sites:

- Probe 1. Lactated Ringer's only (control)
- Probe 2. Lactated Ringer's + Ascorbate
- Probe 3. Lactated Ringer's + Tempol
- Probe 4. Lactated Ringer's + Apocyanin

Initially, we set the local heaters to 34°C (93°F), and only Ringer's perfuses each probe. We collect baseline data for 20 minutes, then we add the investigative substances to the probes. After a second 20-minute baseline, we increase the temperature of the local heaters 0.5°C/5 sec to a target local skin temperature of 42°C (107.6°F). We clamp the local temperature at 42°C (107.6°F). When the SkBF stabilizes, we add L-NAME to all probes to allow for the quantification of NO-dependent vasodilation. After the SkBF stabilizes (~40 minutes), we switch perfusates at all MD sites to Ringer's + sodium nitroprusside (SNP) for about 30 minutes. Heating and SNP perfusion causes maximum vasodilation.

[figure not shown]

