- c. Then the experiment is over, and we remove the MD tubing from the skin and place sterile bandages over the sites. If the subject desires, we can also place a bag of ice on the site for 10 minutes to reduce any bruising that may occur. We measure blood pressure and heart rate before the subject departs.

4. Baseline Experiments – “Day 2”

- a. MD: Acetylcholine (ACh) Dose Response

We prepare 5 MD sites:

- Probe 1. Lactated Ringer's only (control)
- Probe 2. Lactated Ringer's + LNAME
- Probe 3. Lactated Ringer's + Ascorbate
- Probe 4. Lactated Ringer's + Tempol
- Probe 5. Lactated Ringer's + Apocyanin

We clamp the temperatures of the local heaters at 34°C (93°F). When the experiment begins, the subject rests for a 20-minute baseline. When SkBF readings are stable, we add the test substances to probes 3, 4, and 5 as indicated above for about 60 minutes. After 30 minutes, we add LNAME to probe 2. During this time, we obtain a second baseline for about 20 minutes. When the SkBF is stable, we add the first concentration of ACh to the perfusate at each probe. Each site receives 11 increasing concentrations of ACh ($10^{-8}M$ to $10^{-1}M$) each perfused for 5 minutes. As SkBF stabilizes with the addition of each concentration of ACh, we proceed to the next concentration. After the last concentration of ACh, we switch perfusates at all sites to Ringer's + SNP for about 30 minutes. Heating and SNP perfusion causes maximum vasodilation.

- b. Then the experiment is over, and we remove the MD tubing from the skin and place sterile bandages over the sites. If the subject desires, we can also place a bag of ice on the site for 10 minutes to reduce any bruising that may occur. We measure blood pressure and heart rate before the subject departs.

5. Subjects wait at least 3 days before proceeding with the Controlled Feeding protocols.

C. Controlled Feeding Experiments (the order of the local heating and acetylcholine dose response experiments is randomized)

1. Feeding Protocol

Following baseline experiments outlined above, participants are enrolled in a randomized, cross-over protocol involving 4 controlled feeding periods, each 8 days in duration, (7 days prior to subsequent experiments plus the day

of first experiment). Subjects maintain the assigned feeding protocol through the 2 days of experiments. The feeding protocols are:

- low sodium diet devoid of dairy products (L-Na)
- low sodium diet containing cheese (L-Na+C)

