8.3 Statistical methods

We use within-person experimental design and associated repeated measures ANOVA tests with planned contrasts for our primary functional outcomes. We use multivariate regression analysis with possible ANCOVA to determine which measures of oxidative stress and antioxidant status are correlated with our functional findings. For all experiments, we accept significance at $p<0.05$. We adjust P-values and 95% confidence intervals for the mean difference estimates using Tukey's multiple comparison procedure to account for post-hoc multiple comparison testing and ensure a familywise type I error rate less than 5%. We use residual plots to check modeling assumptions, specifically examining them for nonconstant variances and nonnormality. We analyze data using SAS PROC MIXED, a flexible analytic tool that accommodates a wide variety of analysis of variance and regression models and nested and incomplete data structures.

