10.0 Data and Safety Monitoring Plan

NA

- 10.1 Periodic evaluation of data**
- 10.2 Data that are reviewed**
- 10.3 Method of collection of safety information**
- 10.4 Frequency of data collection**
- 10.5 Individuals reviewing the data**
- 10.6 Frequency of review of cumulative data**
- 10.7 Statistical tests**
- 10.8 Suspension of research**

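### Does the planned look at 8 subjects push the error rate of the microdialysis-site contrasts above 5%?

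*Combined protocol and SAP*

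**What the plan says.** Section 8.2 gives separate sizes for separate questions. The comparison between diets is sized at 14 subjects (ANOVA, power 0.80, alpha 0.05). For differences between microdialysis sites, by one-sample t-test and for an effect of 15%, it says that "sample sizes of 8 and 7 subjects per group would be sufficient to detect a meaningful difference". The same paragraph also names 8 subjects for its cheese and sodium data. It then says "We suggest testing 15 subjects through all of the dietary interventions", and continues: "We would plan to perform preliminary analyses after testing 8 subjects to reach our desired statistical power for detecting within group differences between microdialysis sites".

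Section 8.1 gives 25 to be enrolled and 15 needed to complete.

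Section 8.3 sets one level: "For all experiments, we accept significance at" p<0.05. Tukey's procedure is used "to account for post-hoc multiple comparison testing and ensure a familywise type I error rate less than 5" per cent.

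Section 7.2 defines the sites. For local heating, "We prepare 4 MD sites"; for the acetylcholine dose response, "We prepare 5 MD sites".

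Section 10.0 is marked not applicable, so "10.7 Statistical tests" is a bare heading. Section 19.7 concerns the safety of individual subjects. Neither bears on this analysis.

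**The concern.** The early analysis falls at a sample size that the plan itself calls sufficient for a t-test of the site contrasts, and its stated purpose is statistical power. That reads more like a test than a description. The study then goes on to 15 subjects, and Section 8.3 has one significance level for everything. Nothing says whether a site contrast examined at 8 is examined again at 15, or which result is reported.

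Tukey's method handles several comparisons within one analysis. It does nothing for the same comparison made twice as data accumulate. An analyst who tested at both points and kept whichever result was significant would exceed the 5% familywise rate in Section 8.3. The ascorbate, tempol, apocynin and L-NAME sites supply mechanistic support for Hypotheses 1b and 2a, so a reader has reason to ask what error rate a reported site difference carries.

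**Working it through.** **Inputs.** From Section 8.2: look at n=8, full set n=15, one-sample t-test, effect 15%. From Section 8.3: alpha 0.05. From Section 7.2: 4 and 5 sites. Assumed: two-sided tests, since the plan does not state sidedness.

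**1. The plan's own sizes.** Section 8.2 gives neither an SD nor a power for the site contrasts, so 8 and 7 cannot be reproduced. They can only be solved backwards. Power comes from the noncentral t distribution with n−1 degrees of freedom and noncentrality d√n. Assuming 80% power:

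- n=8 needs d=1.156, so the SD of the differences is 15/1.156 ≈ 13.0.
- n=7 needs d=1.273, so the SD is 15/1.273 ≈ 11.8.

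The error rates below are calculated under the null hypothesis and do not depend on the SD.

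**2. One test.** With 20,000,000 simulated null trials, P(p<0.05) is 0.050 at n=8 and 0.050 at n=15.

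**3. Two tests, either one counting.** The first 8 subjects are part of the 15, so the two statistics have correlation √(8/15) = 0.730.

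- Normal approximation: 1 − P(|Z1| ≤ 1.96 and |Z2| ≤ 1.96) = 0.082.
- Simulated t-tests with 7 and 14 degrees of freedom: 0.084. This is 0.050 from the test at 15 plus 0.034 from contrasts significant only at 8.
- If the looks were independent, the figure would be 1 − 0.95² = 0.0975. The overlap in the data makes that an overstatement.

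**4. Tukey at both looks.** This assumes all pairwise site comparisons within one diet and spherical errors, neither of which the plan specifies. With 2,000,000 null trials for each case:

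| Sites | Familywise, one look | Familywise, either look | One given contrast, either look |
|---|---|---|---|
| 4 | 0.050 | 0.085 | 0.019 |
| 5 | 0.050 | 0.085–0.086 | 0.012 |

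The range for 5 sites covers two separate simulations.

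**5. The rule against the text.** The 8.4% needs two conditions: the same contrast is tested at both sizes, and a rejection at 8 stands even if the result at 15 is not significant. The text admits three courses:

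- The look at 8 is preliminary and inference is made at 15: error 5%.
- Site contrasts are tested once, at 8, and the remaining subjects serve the diet comparison sized at 14: error 5%.
- Both are tested and either counts: error 8.4%.

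Section 8.2's own word for the early work is preliminary, which points to the first course. Its remark that 7 or 8 subjects suffice is compatible with the second. Section 8.3 gives a significance level but does not say that a test is repeated, or that an early rejection survives a later null result. Even if both tests were run, reporting the result at 15 would keep 5%.

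**6. What the third course would gain.** A contrast with 80% power at n=8 has 98.6% power at n=15 with alpha 0.05. If 80% is assumed at n=7, power at n=15 is 99.5%. Waiting for the full set therefore loses almost nothing, and analysts have little reason to prefer the smaller sample.

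**The case for a change.** The strongest opposing case is that the word preliminary does not settle the matter, because the stated purpose of the look is power to detect differences, and a look placed where a test is said to be adequately powered may well be used as a test. One sentence would close the gap at no cost to enrolment, procedures or alpha, and writing it before the 8-subject data are seen would remove any later choice between results. Nor is it a full answer that the 5% statement is worded for post-hoc comparisons: with Tukey at both looks, that same familywise rate would be about 8.5%.

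Much of this stands. The plan does not say whether the early analysis is inferential, no other section does, and the two-look figures are correct under their assumptions. What does not stand is the step from silence to inflation. The rule that either result counts has to be supplied by the reader. No stopping, dropping of a contrast, change in sample size or early reporting depends on the look, and Section 8.1 requires 15 completers. The added sentence would only record the ordinary meaning of a preliminary analysis. An alpha-spending boundary would serve a testing rule that the plan has not adopted.

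**Conclusion.** No change follows. The omission is real but small: a missing detail that analysts would fill by treating the 8-subject analysis as preliminary and drawing conclusions once. Done that way, the type I error for a site contrast is 5%. The excess of 3.4 percentage points (8.4% against 5%, two-sided, one contrast) arises only under a test-twice, either-counts rule that the plan does not contain. The Tukey figure of about 8.5% rests further on all pairwise comparisons and spherical errors. In either case the exposure is confined to supporting mechanism contrasts. The stated purpose of the early look does not extend to the diet comparison, on which Hypotheses 1b and 2a mainly rest. This conclusion depends on taking preliminary in its usual sense; if a claim of significance were to be made from the 8-subject data and the same contrast tested again at 15, the two-look calculation would apply.

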8.3 Statistical methods

We use within-person experimental design and associated repeated measures ANOVA tests with planned contrasts for our primary functional outcomes. We use multivariate regression analysis with possible ANCOVA to determine which measures of oxidative stress and antioxidant status are correlated with our functional findings. For all experiments, we accept significance at $p<0.05$. We adjust P-values and 95% confidence intervals for the mean difference estimates using Tukey's multiple comparison procedure to account for post-hoc multiple comparison testing and ensure a familywise type I error rate less than 5%. We use residual plots to check modeling assumptions, specifically examining them for nonconstant variances and nonnormality. We analyze data using SAS PROC MIXED, a flexible analytic tool that accommodates a wide variety of analysis of variance and regression models and nested and incomplete data structures.

9.0 Confidentiality, Privacy and Data Management

9.1 Confidentiality

9.1.1 Identifiers associated with data and/or specimens

Most of the data are coded and do not contain personal identifying information. Documents allowing identification of participants do not leave our labs and are only available to authorized persons. The names and contact information that potential subjects submit via the secure Qualtrics website is copied to a password-protected lab computer. The subjects' information is deleted immediately from the Qualtrics website after being copied. Only authorized personnel may access the lab computer. Data forms containing identifiable information are shredded when no longer needed (within 6 years after publication of results).

9.1.1.1 Use of Codes, Master List

We keep data in the laboratory in locked cabinets, the password-protected folder on the secured PSU server, and on password-protected computers maintained in a locked room. Only authorized personnel have access. Coded data shared with unauthorized persons cannot be traced to individuals. The list linking code numbers to participants is not

shared with unauthorized persons and destroyed when project is completed and published. The code is destroyed within 5 years of publication of the data.

9.1.2 Storage of Data and/or Specimens

We maintain data in the laboratory in locked cabinets and on password-protected computers located in rooms that are locked when unoccupied. Most of the data are coded and do not contain personal identifying information. Documents allowing identification of participants do not leave the investigator's labs and are only available to authorized persons. Coded data shared with unauthorized persons cannot be traced to individuals. We store any list linking the code to participants' identity in locked cabinets and on password-protected computers located in rooms that are locked when unoccupied. Potential participants may submit pre-screening questionnaires via the investigator's website / Qualtrics (commercial survey website). All web traffic to and from the Qualtrics application is done via a Secure Socket Layer (SSL) that encrypts the data in transmission. Qualtrics deletes data from their servers within 24 hours after the user deletes it from the website. Hard copy data forms containing identifiable information are shredded when no longer needed (within 5 years after publication of results). Screening data from subjects who are not accepted into the study are shredded when the project ends. Subjects may give permission to have their contact information retained in the investigator's secured files if they wish to be considered for participation in future studies. After we complete the study, we remove all identifiers from the study's data and store the data indefinitely. Individual data may be used without identifying the subject to illustrate representative responses.

Biological specimens are stored at University Park and Quest Labs, (Chantilly, VA), Ohio State University (Columbus, OH), and Georgia Health Sciences University (Augusta, GA). At University Park, the specimens are stored in a -80°C freezer in Noll first floor hallway. All specimens not exhausted upon analysis are maintained no longer than 5 years after publication.

9.1.3 Access to Data and/or Specimens

Only authorized personnel have access.

9.1.4 Transferring Data and/or Specimens

Some specimens are mailed or transported by lab members or couriers of outside labs for analysis. All specimens are coded and do not contain identifiers. We do not share the code with unauthorized persons. The outside labs are at Quest Diagnostics (Chantilly, VA), Ohio State University (Columbus, OH), and Georgia Health Sciences University (Augusta, GA).

9.2 Subject Privacy

We tell participants that they may decline to answer questions and decline to participate in the study. Only authorized personnel are present during screening and experiments. On occasion (e.g. educational visit, visiting colleague, site visit) participants may give permission for visitors to observe a procedure or experiment.

10.0 Data and Safety Monitoring Plan

NA

- 10.1 Periodic evaluation of data**
- 10.2 Data that are reviewed**
- 10.3 Method of collection of safety information**
- 10.4 Frequency of data collection**
- 10.5 Individuals reviewing the data**
- 10.6 Frequency of review of cumulative data**
- 10.7 Statistical tests**
- 10.8 Suspension of research**

11.0 Risks

General note: The research group's members are trained and competent in their duties. The group, led by [name], evaluates the effectiveness and safety of protocols and procedures in an ongoing fashion. We discuss the protocol with candidates, invite questions, and offer tours of the laboratory. Prior to medical screening, candidates read

and sign informed consent forms detailing protocols, procedures, risks, sensations, compensation, etc. We give candidates witnessed copies of the signed consent forms. After accepting participants into the study, we discuss and review the procedures and protocols with them generally and at each step throughout the project. We frequently remind participants of the option to withdraw from the study at any time. Restricting access to experiments, data, and coding to authorized personnel maintains confidentiality. The Noll Lab's electronics technician certifies the electrical devices for human use. Lists of emergency numbers remain by lab telephones. At least one cell phone is present at each experiment. A hospital and emergency medical services are within 1-2 miles of the lab. An AED is located nearby in the hallway.

Microdialysis: We insert a 25 g needle horizontally into and then out of the layers of the skin of the ventral forearm. The needle's entry and exit are about 2.5 cm apart. We thread the microdialysis "probe," comprising a tube of membrane (320 um OD) with tubing attached at both ends (650 um OD), through the needle. Then we withdraw the needle leaving the membrane under the skin. We perfuse the probe with sterile saline using a syringe pump.

Cutaneous microdialysis commonly causes some pain and bruising similar to that experienced during blood draws. There is usually no pain after the probe is in place. The participant may experience mild pain while we remove probe. Minor bleeding may occur. As with routine venipuncture, a participant who is nervous about needles could have increased heart rate and blood pressure, become lightheaded or nauseated, or could faint.

As with venipuncture or any event that breaks the skin, infection is possible, but proper aseptic technique and sterile solutions / supplies keep the risk minimal. However, no participants in any of our experiments been reported infection. We place a sterile bandage on the site after the experiment.

The persons performing MD have been trained in proper technique and procedure by [name] and had their technique witnessed / approved by [name], D.O. , and/or [name]. (see uploads under respective "CV"s). Ice numbs the skin and the small needle reduces pain during insertion. We stop any bleeding by applying mild pressure to the site with sterile gauze. In the unlikely event that the individual has an allergic reaction, we stop microdialysis immediately. If the reaction becomes severe, we seek emergency medical assistance. Although rare, if the membrane should break in half during removal, we remove the remaining half by gently pulling the attached tubing. This presents no additional risk to the participant. In the unlikely event in which the membrane breaks during removal leaving an isolated piece of membrane under the skin, we treat the piece of membrane in a manner similar to that for a splinter in the skin. In this case, we may have to make a superficial incision for removal. Such an event has not occurred in projects that have used MD in this lab (over 1,000 MD probes have been placed by [name], alone).

Perfusate: Lactated Ringer's solution flows through the microdialysis probes. An allergic reaction to this physiological saline solution is highly unlikely.

All substances (ACh, Apocynin, Ascorbate, L-NAME, SNP, Tempol) added to the lactated Ringer's perfusing the microdialysis probes have been used previously clinically and/or in research in humans.

Microdialysis delivers small amounts of the substances to a nickel-sized area of the skin. The small quantities used and the extremely localized administration during microdialysis does not produce systemic effects. To our knowledge, there are no reports of long or short-term side effects of these substances administered through microdialysis. The chance of adverse reactions to these substances is extremely small given the minute amount delivered to the a very small area of skin, the lack of adverse reactions to similar amounts delivered via MD in many other studies, and lack of adverse effects in human cell cultures. There is a slight chance of allergic reaction to these substances that could produce redness, itching, rash, and/or swelling. A severe reaction (anaphylactic shock) could also cause fever, difficulty in breathing, changes in pulse, convulsions, and/or loss of consciousness.

The perfusate is sterile. We prepare the perfusate in their laboratory using sterile techniques and supplies commonly used for this purpose in research laboratories. The Ringer's solution is sterile as purchased. We add other solutions aseptically to the sterile bag of Ringer's solution through 0.2 micron Gelman Sterile Acrodisc syringe filters. We mix the

perfusate for same-day use and discard excess perfusate after the experiment. During the IND application process, the FDA accepted the researchers' technique for preparing perfusates. Although unlikely, in the case of a severe reaction to the perfusate, the researchers call 911.

Laser Doppler Flowmetry: The probe attaches to the skin with double-sided tape and measures skin blood flow in a 1mm³ volume of skin. Weak lasers can hurt the eye if one should stare into the light for a long time. The red light seen on the surface of the skin is harmless. We do not turn on the laser until they tape the probes to a surface. We remove the tape afterward carefully. We have used this technique in their lab with IRB approval for many years without incident.

Blood pressure (manual and Cardiocap): The manual and Cardiocap methods use a cuff that inflates on the upper arm. The cuff slowly deflates while we listen to the pulse-sounds at the inside of the elbow with a stethoscope or the Cardiocap monitors the pulse through the cuff. The inflated cuff may make the arm feel tingly and numb, and the cuff may temporarily bruise the arm. Efficient and competent measurement technique minimizes the duration of cuff inflation. These techniques to measure blood pressure are unlikely to produce lasting ill effects.

Povidone Iodine: Hospitals and researchers use povidone iodine to clean and sterilize the skin. Participants could be allergic to iodine. An allergic reaction could cause redness, itching, rash, and/or swelling. A worse reaction could also cause fever, breathing problems, changes in pulse and/or blood pressure, convulsions, shock, and/or loss of consciousness. We use only alcohol on participants with iodine allergy as identified during screening.

Blood draw: Blood draws can cause anxiety (with increased heart rate and blood pressure), mild pain, swelling, nausea, lightheadedness, fainting, or bleeding. There is a slight chance of infection. A competent nurse performs blood draws using standard venipuncture-procedure and techniques that minimize the chance of infection. Participants may recline for the procedure.

Tape and adhesive disks: Participants could be sensitive to the adhesive of the tape and double-sided adhesive disks used in the study causing redness, rash, tenderness, and/or itching. We remove the tape and adhesive disks carefully. Ointment is available, if needed.

Screening: The screening includes blood sample, height, waist circumference, weight, heart rate, blood pressure, pregnancy test, and history performed by the competent research staff. Participants may be uncomfortable giving medical information or being measured. The participants may decline to answer questions or participate in measurements. We conduct screenings professionally and privately.

Initial Screening Form: We use the form to initially determine a candidate's suitability for the study. The initial interview gathers minimally invasive personal data that is kept confidential. We used similar interviews in the past without problem. Candidates may complete the form at the lab group's web site via the Qualtrics commercial survey website. The participant may decline to answer questions. We conduct phone interviews professionally and privately. Only authorized personnel may access completed forms.

ECG: We attach three to twelve electrodes to the participant's chest and then attach the electrode wires to a ECG machine. The machine records the electrical activity of the heart. There are no adverse effects from this measure. A participant may be shy about electrodes applied to the chest. We carefully remove the tape afterward. We conduct the test professionally and privately.

Thermoregulation Lab Website: Potential participants may enter data into the screening form (see above) via the Qualtrics website. Qualtrics is a secure website and survey application designed to support data capture for research studies. The participant may be concerned about data's security. All web traffic to and from the Qualtrics application website is done via a Secure Socket Layer (SSL) that encrypts the data in transmission. The questionnaire contains statements advising of the limitations of technology and that there is no confidentiality guarantee. Data is deleted from

the Qualtric's servers within 24 hours after the user deletes it from the website. Participants may choose a personal interview instead.

Local Heating: The local heating control unit (Moor Instruments) precisely controls and monitors the temperature of the heated probe holders used with the Laser Doppler Flowmeter. To determine the maximal SkBF, we increase the temperature of the heating units slowly (about 0.1°C every 1 second). The skin feels very warm but not painful. Local heating causes temporary redness of the skin that subsides within several hours. This technique is very unlikely to produce long-term ill effects. The local heating controllers (Moor Instruments) precisely control and monitor the temperature of the heated probe holders. The system has programmed maximum temperature limits. This technique is unlikely to cause long-term ill effects.

Latex: Some gloves and medical materials are made of latex rubber. Some people may be sensitive to latex. **Latex:** Screening identifies and excludes candidates having a known latex allergy.

Controlled Feeding Protocol: It is possible that the subject could have a food allergy. Food allergies can produce redness, itching, rash, and/or swelling. A severe reaction (anaphylactic shock) could also cause fever, difficulty in breathing, changes in pulse, convulsions, and/or loss of consciousness. To avoid known food allergies, screening for this study includes identification of known allergies, including food allergies. Also, subjects meet with a registered dietitian prior to participating to identify food preferences. If a subject is allergic to the investigative substances, she/he is excluded from the study. If a subject is allergic to a substance that may be appropriately substituted with another, we make the substitution, otherwise we exclude the subject from the study.

Flow Mediated Vasodilation (FMD) Test / Doppler Ultrasound: There is a small chance the probe could irritate the skin. Placing the probe on the arm's skin may cause temporary minor redness. The inflated cuffs may cause the participant's arms and feet to feel numb or tingly, and the skin's color to change slightly. The cuffs could cause mild bruising. The gel is the same as that used with medical ultrasound tests. The gel may feel cool or cold on the skin. A bad reaction to the gel is highly unlikely. The cuffs inflate for a minimal amount of time. The temporary redness from the probe is unlikely to have lasting ill effects. The participant may decline the test.

Sublingual Nitroglycerine: Subjects may experience some of the following reactions to the nitroglycerine

headache	lightheadedness	dry mouth	flushing
irregular heart beat	weakness	nausea	vomiting
5-10 minute drop in blood pressure	fainting	dizziness	sweating

Subjects may notice a sweet taste and/or tingling sensation in the mouth while the tablet dissolves. All these effects are usually short-lived. We minimized the effects by having subjects remain supine for 20 minutes after receiving the tablet. In subjects who experience a drop in blood pressure, values usually return to within 10 mmHg of baseline levels upon resolution of the testing. We monitor subjects for up to an hour after they receive the nitroglycerin if they have a strong or bad reaction. Subjects could have a mild or severe allergic response to the drug. This response could include rash, itching, difficulty breathing, and swelling of the face, lips, tongue, or throat. In the event that blood pressure does not return to baseline, coupled with related symptoms, we refer subjects for medical follow-up. In the event of a severe reaction (e.g. anaphylaxis) we call 911.

The effects of nitroglycerin on pregnant or nursing women are unknown. We exclude subjects who are pregnant or nursing. The use of nitroglycerin for artery measurements is not an FDA-approved use of this drug. However, nitroglycerin has been used in this way in many research studies nation-wide without problem. Also, sublingual nitroglycerin is often prescribed for and self-administered by heart patients who have, or are at risk for, angina (heart pain).

Fasting: Subjects may feel hungry during the fasting period and for the duration of experiment. We have conducted many research protocols over the years in which subjects were required to fast 8 hours prior to and then during experiments. In the vast experience of the medical research staff and investigators, there is no risk of fainting due to fasting for this length of time.

